1. To gather additional safety and efficacy data and reaffirm that using the CVS device leads to a significant reduction in migraine headache days relative to a placebo.
2. To extend the treatment period from 3-months to 6-months, with all subjects (including placebo) receiving active treatment in the second 3-month period.
3. To test the efficacy of once-per-day active treatments versus twice-per-day active

treatments.

4. To evaluate the durability of gains realized after the end of the treatment period through an additional 3-month long headache diary period.

All participants will be subjects whose response to prior therapies has been partially successful, but limited. As defined in detail below, under International Headache Society (IHS) guidelines all of these subjects will be classified as “episodic” or acute. None will be classified as “chronic.” In assessing the effectiveness of the CVS device, the study will consider both (1) a subject’s number of headaches as well as (2) the severity of each and of all of those headaches. The primary endpoint is based on outcomes data collected during the treatment period vs. the pre-treatment baseline period, focusing on the comparative number of migraine headache days.

Description of the Treatment Paradigm and Study

1) Intended Use/Indication for Use

- **Intended Use:** The CVS device is intended to stimulate the vestibular system via external ear canals using controlled thermal waveforms.
- **Indication for Use:** The CVS device is indicated for use in the prevention of episodic migraine headache.

2) Subject Selection Criteria Pre-Treatment Data

In working with and through their respective designated assistant(s)/coordinator(s), the principal investigators will identify and screen potential participants, all of whom will have previously been diagnosed as episodic migraine headache subjects. The investigators will review the subjects' medical records to select those individuals who they identify as meeting the inclusion criteria for participating in the study.

- **Inclusion Criteria:** Each participant must have a pre-treatment history that, when initially screened by a principal investigator or designee, documents that she/he meets all elements of the following:

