Less likely:

- Nausea/vomiting

- Headache
- Coughing

All of these side effects are expected to resolve once use of the device is stopped.

7) Study Endpoints

- **Primary Efficacy Endpoint for the Study**

For the twice-per-day active-treatment subjects: During the third month of the first treatment period, their average total number of monthly migraine headache days will be lower than their comparable averages derived from the pre-treatment baseline period. Also, this reduction in migraine headache days will exceed that observed in the twice-per-day placebo group.

- **Secondary Endpoints:**

- The normalized percent-reduction in migraine headache days (during the third treatment month relative to the pre-treatment baseline) in the BID active-treatment subjects will be compared to that of the BID placebo-treatment subjects. Groups will be compared on the basis of percent-change (continuous variable) as well as the “50% responder rates” (discrete variable).
- The reduction in acute (prescribed) medication taken (during the third treatment month relative to the pre-treatment baseline) in the BID active-treatment subjects will be compared to that of the BID placebo-treatment subjects.
- The reduction in subject-perceived headache pain scores (during the third treatment month relative to the pre-treatment baseline) in the BID active-treatment subjects will be compared to that of the BID placebo-treatment subjects.
- To assess whether active treatment results in improved quality of life (related to the reduction in migraine), HIT-6 change scores (end of the first treatment period versus baseline) will be compared across BID active-treatment subjects and BID placebo-treatment subjects.
- To assess whether active treatment results in improvements in depression or anxiety, BDI and BAI scores (end of the first treatment period versus baseline) will be compared across BID active-treatment subjects and BID placebo-treatment subjects.
- To assess whether active treatment results in improved sleep quality, Pittsburgh Sleep Quality Assessment change scores (end of the first treatment period versus baseline) will be compared across BID active-treatment subjects and BID placebo-treatment subjects. Correlational analysis will be performed to determine whether a relationship exists between improved sleep and reduced migraine frequency.

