An experienced, independent and blinded Statistician will analyze and summarize the daily headache diaries for all subjects and evaluate the primary endpoint and observational aims. A blinded reviewer will analyze and summarize the quality of life data.

The primary aim of this trial is to determine if subjects randomized to the twice-daily active group, have a greater reduction in the number of headache days than those assigned to the twice-daily placebo group. For this study, the reduction in headache days (primary endpoint) is calculated as the number of headache days during the baseline month minus the number of headache days during treatment month three. An intent-to-treat methodology will be employed for the primary aim; however, per protocol analyses will also be conducted for comparison. Analysis of the primary endpoint and the secondary headache-related endpoints assessed in the daily diary will be performed for all subjects that complete at least 25 diary entries or more during the relevant 28-day treatment month. Treatment compliance is defined as completion of at least 50% during

each treatment months (for the per protocol evaluation). Subjects with treatment compliance below 50% during any treatment month will be assigned to the intent-to-treat group only. As accurate assessment of some of the secondary endpoints assessed during study period do not depend on daily headache diary compliance, treatment compliance will be the only criteria for inclusion in the per protocol analysis of those secondary outcomes. Statistical significance will be defined with a Type I error of 5% ($\alpha=0.05$). Wilcoxon rank-sum tests (for non-normal data) or a paired student's t-tests (for normal data) will be used to establish whether the reductions in headache days between the baseline and third treatment month in each treatment arm are statistically significant. Mann-Whitney U tests (for non-normal data) or unpaired student's t-tests (for normal data) will be used to determine whether the reduction in migraine headaches in the twice daily active treatment arm subjects is significantly greater than that observed in the twice daily placebo treatment arm subjects. No interim analyses of efficacy are planned.

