The study is powered for the primary aim. Given a sample size of 40 subjects per arm and a standard deviation in the reduction of headache days of $\sigma=3.36$, a mean difference for the reduction in the number of headache days between the twice-daily active arm and the twice daily placebo arm of 2.13 days will be detectable at the 95% significance level ($\alpha=0.05$) with 80% power. The figure below shows the sensitivity of the detectable differences relative to the value of the standard deviation and the sample size.

The study is intentionally overpowered for the primary endpoint (based on the mean reduction of 2.73 headache days in the first RCT), however, a sample size of 40 subjects per arm should allow for sufficient power to assess the majority of secondary endpoints at

the end of the sixth treatment month and at the end of the post-treatment observation period given the expected dropout rate of 5 subjects per group during each 3 month period. Notably, while the 50% responder rate (a secondary outcome) will be evaluated as a discrete variable, it is unlikely to yield statistical significance due to insufficient sampling. Therefore, the similar measure of percent-change in migraine days will also be compared as a continuous variable across groups.

An analysis will be conducted to determine if blinding was successful using descriptive statistics.

9) Quality Assurance Monitor

A quality assurance monitor will be used to audit study sites. Following written procedures, the monitor will verify that the clinical trial is conducted and data are generated, documented and reported in compliance with the protocol, GCP and applicable regulatory requirements. Investigational site(s) will provide direct access to all trial related sites, source data/documents and reports for the purpose of monitoring and auditing by the sponsor and inspection by regulatory authorities.

10) Procedures for adverse events:

- **Documentation and assessment**
 - Following the informed consent process, clinical study subjects will be routinely questioned about adverse events at study visits and telephone contacts by the clinical research sites. All adverse events, regardless of treatment group, or suspected causal relationship to the investigational device, will be recorded in the subjects' case report forms in their study binder.

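### Section 8 computes the primary endpoint from headache days, but the declared primary endpoint is migraine headache days, a narrower and separately defined variable

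*Combined protocol and SAP*

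**What the plan says.** The declared endpoint is consistent in two places. The Background describes the primary endpoint as "focusing on the comparative number of migraine headache days". Section 7, under the primary efficacy endpoint, requires for the twice-daily active arm in month three that "their average total number of monthly migraine headache days will be lower than their comparable averages derived from the pre-treatment baseline period", and that the reduction exceed the one seen on placebo.

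Section 8 changes the variable:

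- Primary aim: whether twice-daily active subjects "have a greater reduction in the number of headache days than those assigned to the twice-daily placebo group".
- Calculation rule: "the reduction in headache days (primary endpoint) is calculated as the number of headache days during the baseline month", minus the corresponding count in treatment month three.
- Within-arm tests: "whether the reductions in headache days between the baseline and third treatment month in each treatment arm are statistically significant".
- Between-arm test, in the same paragraph: "whether the reduction in migraine headaches in the twice daily active treatment arm subjects is significantly greater". This is a third wording, which names neither defined day count.
- Power statement: "a standard deviation in the reduction of headache days" of 3.36, with the planning effect "based on the mean reduction of 2.73 headache days in the first RCT".

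The Definitions keep the two day counts apart. A Headache Day is any day with head pain that the subject scores from one to ten, with no minimum duration. A Migraine Headache Day needs a migraine lasting 30 minutes or more; the subject judges whether a headache is a migraine, and headaches treated with prescribed acute medication count as migraine. The inclusion criteria limit the two counts separately, and every diary form asks about them in separate questions.

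**The concern.** Every migraine headache day is also a headache day, but not the reverse. A statistician who follows the Section 8 formula to the letter would therefore analyse a broader variable than the one on which the trial is to be judged. Both counts can be derived from the diary and both are attached to the primary endpoint somewhere in the plan, so the primary variable is open to choice until the wording is settled. There is a time limit: Sections 4 and 7 have the baseline and first treatment period analysed as a complete trial once 120 subjects finish that period, while the rest of the study is still running.

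The power statement has the same problem. Its SD and effect carry the headache-day label, so on its face it does not describe the declared endpoint.

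**Working it through.** **1. Are the two variables really different?** Inputs: the Definitions, and the inclusion criterion of 4 to 14 headache days a month, of which 4 to 14 are migraine days. The baseline gap per subject (headache days minus migraine days) is at least 0 and at most 14 - 4 = 10.

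Take a subject at the outer limit, with 14 headache days at baseline, 4 of them migraine:

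| Month-three outcome | Headache days | Migraine days | Reduction by Section 8 formula | Reduction by Section 7 endpoint |
|---|---|---|---|---|
| The 4 migraines become non-migraine headaches | 14 | 0 | 14 - 14 = 0 | 4 - 0 = 4 |
| The 10 non-migraine days disappear | 4 | 4 | 14 - 4 = 10 | 4 - 4 = 0 |

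The formula can understate or overstate the declared endpoint. The documents do not give the typical gap between the counts, so neither the direction nor the average size of the error can be computed.

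**2. Which variable was intended?** The Background reports the first trial's month-three change in migraine days as -3.6 (active) and -0.9 (placebo). The difference is 3.6 - 0.9 = 2.7 days. Section 8 gives the first trial's effect as 2.73 and calls it headache days. The agreement suggests that Section 8 means migraine days.

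**3. Does the power figure reproduce?** Inputs from Section 8: 40 per arm, SD 3.36, alpha 0.05, 80% power. Sidedness is not stated. With a two-sided unpaired t-test (noncentral t), the detectable standardised difference at 40 per arm is about 0.634. The detectable difference is 0.634 × 3.36 = 2.13 days (2.131 unrounded), which is the plan's figure; power at exactly 2.13 days is 79.95%. A one-sided test does not fit (88.3% power under the normal approximation). Power at 2.73 days is 94.8%, in line with the plan's remark that the study is overpowered. The arithmetic is sound.

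**4. What if 3.36 is not the migraine-day SD?** No separate SD is given for the two variables, so the other rows below rest on assumed values and are illustrations only. Detectable difference is 0.634 × SD.

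| Migraine-day SD | Detectable difference, 80% power | Power at 2.73 days |
|---|---|---|
| 3.0 (assumed) | 1.90 | 98% |
| 3.36 (as stated) | 2.13 | 95% |
| 4.0 (assumed) | 2.54 | 85% |
| 4.5 (assumed) | 2.85 | 76% |

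**The case against.** The best reply is that Section 8 uses headache days as shorthand. Section 7, under an explicit heading, already gives the variable, the time window and the contrast. Its closing text, just before Section 8, refers to the stated primary endpoint and so points back to that definition. The deciding between-arm test is at least worded in terms of migraine. The secondary endpoints in Section 7 are equally loose: percent change is given in migraine headache days in one item and in monthly headache days in others, and a dose-response aim about migraine days is analysed on total headache days. The statistician is blinded to assignment, the table's outer-limit subject is an extreme, and counting prescription-treated headaches as migraine narrows the gap between the counts. No passage suggests that 3.36 belongs to another variable, and Section 8 refers to a sensitivity figure that could not be seen here.

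Much of this stands. A drafting slip is the likeliest explanation, no sample size error is shown, and the remark that 3.36 has no stated source applies only to the readable text. But the shorthand reading gives a defined term a second meaning. The inclusion criteria, and the rule for grouping subjects who exceed 14 headache days, use the term in its strict sense. The one explicit subtraction formula, tagged as the primary endpoint, names the wrong defined term, and the intended variable has to be inferred by matching two planning figures. Blinding to assignment does not settle which variable is primary.

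**Conclusion.** The concern holds. The primary-endpoint formula in Section 8 is wrong as written, because it yields a different variable from the endpoint declared in the Background and Section 7. The two baseline counts can differ by 0 to 10 days per subject; the effect on the trial result is unknown in direction and size. That migraine days were intended is an inference from 2.7 against 2.73, not something the plan states. The 2.13-day detectable difference is correct arithmetic, assuming a two-sided test, and it applies to the declared endpoint only if 3.36 is the migraine-day SD. This must be corrected before the first-period analysis because it concerns the identity of the primary variable.

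**What to change.** Before the first-period analysis:

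- In Section 8, replace *headache days* with the defined term *migraine headache days* in the primary aim, the calculation rule and the within-arm tests. Replace *migraine headaches* with the same term in the between-arm test. The rule becomes: migraine headache days in the baseline month minus migraine headache days in treatment month three.
- In the power statement, say which variable SD 3.36 and effect 2.73 come from. If 3.36 is the migraine-day SD, relabel it, and 2.13 days at 80% power stands. If not, restate the detectable difference with the migraine-day SD.
- In the same pass, check the Section 7 secondary endpoints that move between the terms, and name the intended variable in each.

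The cost is an edit to the wording and one confirmation from the sponsor. The diary already collects both variables, so no new data are needed and the sample size does not change.

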- have a cochlear implant
- have chronic tinnitus
- have temporomandibular joint disease
- have been diagnosed with traumatic brain injury
- have been diagnosed with neurological disease other than headaches

- have a diagnosed vestibular dysfunction and/or balance dysfunction
- have a history of abusing alcohol or other drugs
- are experiencing medication overuse headaches (individuals with respect to whom the principal investigator is concerned that analgesic abuse is involved based on the ICHD-II guidelines).
- are less than 18 years old or greater than 65 years old
- have had eye surgery within the previous three months or ear surgery within the previous six months
- have active ear infections or a perforated tympanic membrane
- have participated in another clinical trial within the last 30 days or are currently enrolled in another clinical trial
- are using Botulinum toxin-based treatments for migraines or for facial cosmetic reasons.
- are taking anti-emetics chronically (more than 2 times per week, consistently)
- Though not excluded, subjects taking anti-histamines will be encouraged not to take such medications within four hours prior to a CVS treatment. The investigator should review other medications taken by the subject with properties that mimic anti-nausea or anti-dizziness drugs as these may reduce responsiveness of the vestibular system to caloric stimulation. Such medications should also be avoided within four hours prior to a CVS treatment.

- **Withdrawal Criteria**

- Subjects must be withdrawn from the clinical trial if any of the following events occur:
 - Surgery during the study period.
 - A subject does not continue to meet inclusion/exclusion criteria.
 - A subject is significantly non-compliant with the requirements of the protocol (principal investigator & sponsor decision).
 - The subject does not complete at least 25 of 28 daily diary entries in her/his headache diary during the baseline period. (That is, the subject must be compliant with maintaining the headache diary.)
 - A subject becomes pregnant during the trial as evidenced by a positive pregnancy test.
 - The subject develops an illness (adverse event) that would interfere with his/her continued participation.
 - The subject withdraws his/her consent.
 - The principal investigator feels that it is the subject's best interest to be withdrawn.
 - Scion Neurostim discontinues the study or has achieved the targeted enrollment.

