If the subject is discontinued from the participation in the study for any reason, the principal investigator must make every effort to perform all evaluations for the final visit and document the reasons for discontinuation. If a subject withdraws due to an adverse event, the study coordinator will follow up with regular phone calls to document the resolution of the event.

Though a subject will not be withdrawn from the study if she/he exceeds 14 headache days in any of the treatment months, such subjects will be grouped separately during the final study analysis. The rationale for this grouping is that a large percentage of subjects in the first CVS migraine RCT were excluded from randomization because they exceeded 14 headache days, thus calling into question their stable episodic status. If a subject has a “good month” during baseline, but is potentially unstable, she/he might be recruited into the study in violation of the aim of enrolling stable EM subjects. No evidence that the CVS device increased headache burden was seen in the first RCT. However, we will continue to follow subjects who exceed 14 headache days in a month during the treatment period so as to gather more data on this sub-population.

- **Concomitant Medications**

- The use of acute abortive medications for the symptomatic treatment of migraine headache will be allowed during the clinical trial. Subjects may use their usual acute abortive medications, and medications should not be changed during the clinical trial. A treated migraine headache is one for which a subject has taken an acute abortive medication (prescription medication, not OTC).
- The subject may be on a single migraine prophylactic drug as long as the dosage has not been altered within three months of starting the study and the dosage must not be altered for the duration of the study. The subject must not have failed on more than two classes of properly administered prophylactic pharmaceutical therapies for migraine headache. Prophylactic medications used to treat other medical conditions may be used, at the principal investigator's discretion, if the subject is taking a stable dose for at least three months prior to screening and continues throughout the study.

3) Pivotal Study Size; Randomization

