- (i) **Screening & Baseline Period:** Once the subject has been established as having the appropriate pre-treatment history, she/he will be asked to complete a review of the informed consent. If the subject agrees to participate in the study, the subject will then complete a screening visit. The study coordinator will complete a headache history questionnaire for the subject. If the subject is recommended for continuation in the study after the screening visit and tentatively approved by a principal investigator, she/he will start a daily headache diary and continue to make entries for twenty-eight consecutive days. Subjects will be given Scion email accounts to be used for submitting headache diary entries. Sites will assist subjects with syncing their Scion email accounts with their smartphones or tablets, and will ensure that subjects can competently take a photo of the ediary form, upload and send according to procedure. If the subject does not complete at least 25 of 28 daily headache diary entries during the baseline period, she or he will be withdrawn and will not proceed to randomization.
- (ii) **Clinic Training Visit:** After enrollment, the completion of one month of daily headache diary entries, and reconfirmation by the relevant investigator of the subject's participation in the study, the subject will come to the clinic for an appointment(s) for training on the use of the CVS device. During the clinic visit, the subject will complete a quality of life (QOL) assessment. The assessment will consist of the HIT-6, BAI, BDI-II and Pittsburgh Sleep Quality Assessment questionnaires. The BAI and BDI-II scores will be tallied with the following outcomes:
 - a. Subjects who score 20 or higher on the BDI-II or answer affirmative to questions 9 on the BDI-form will not proceed to randomization and will be withdrawn from the study.
 - b. Subjects who score 16 or higher on the Beck Anxiety Index will not proceed to randomization and will be withdrawn from the study.

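### The primary analysis is called intent-to-treat but leaves out randomized subjects without a near-complete month-3 diary, and no planned analysis would show the effect of that exclusion

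*Combined protocol and SAP*

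**What the plan says.** Section 8 (Statistical Analysis and Study Size) states: "An intent-to-treat methodology will be employed for the primary aim". Per-protocol analyses are added for comparison. The next sentence says that analysis of the primary endpoint and of the diary-based secondary endpoints "will be performed for all subjects that complete at least 25 diary entries or more during the relevant 28-day treatment month". The primary endpoint is "calculated as the number of headache days during the baseline month minus the number of headache days during treatment month three", so the relevant treatment month is month 3.

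The only stated difference between the two analysis sets is device use: "Subjects with treatment compliance below 50% during any treatment month will be assigned to the intent-to-treat group only".

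Three other places bear on the point.

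- **Baseline diary.** The Withdrawal Criteria in section 2 list this ground: "The subject does not complete at least 25 of 28 daily diary entries in her/his headache diary during the baseline period". Section 4(i) adds that such a subject is lost before allocation: "she or he will be withdrawn and will not proceed to randomization".
- **Non-compliance.** The same Withdrawal Criteria allow removal when "A subject is significantly non-compliant with the requirements of the protocol", by decision of the principal investigator and sponsor.
- **More than 14 headache days.** Section 2 keeps subjects who exceed 14 headache days in a treatment month in the study, but says "such subjects will be grouped separately during the final study analysis".

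**The concern.** An intent-to-treat comparison keeps every randomized subject in the assigned arm. Here, leaving before month 3 or recording 24 days in it removes a subject from both analysis sets. The result is an available-case analysis of diary completers. It estimates the effect in all randomized subjects only if having a near-complete month-3 diary is unrelated to outcome.

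The plan's own forms make related loss foreseeable: the Subject Disposition Form lists lack of efficacy and adverse event among the reasons for discontinuation. The Early Termination Visit form collects adverse events, medication changes, vital signs, an ear exam and questionnaires, but asks for no further diary.

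What is at stake is the trial's single primary comparison. Followed exactly, the plan would report a diary-completer estimate as intent-to-treat, and nothing in it would show the size or direction of the difference.

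A smaller gap sits beside this. The endpoint is a difference of raw counts, months with 25 to 28 entries are accepted, and no rule says how unrecorded days are treated.

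**Working it through.** **1. The plan's own figure.** Section 8 gives 40 per arm, SD 3.36, alpha 0.05, 80% power and a detectable difference of 2.13 days.
- SE = 3.36 × √(2/40) = 0.751.
- A two-sided t test for 2.13 days has 80.0% power. The figure reproduces, so the sample size is not in error.

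**2. Share of subjects lost.** Section 8 expects 5 dropouts per group in each 3-month period. Sections 3 and 7 count the target of 120 as subjects who complete the first treatment period, that is 40 per arm. If the 5 apply to the first period and all lack a usable month-3 diary, 45 are randomized per arm and f = 5/45 = 11.1%. Retained subjects with poor diaries would add to this; the documents give no rate for them.

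**3. Illustration: no reduction in those lost.** The Background gives first-trial reductions of 3.6 days (active) and 0.9 days (placebo). Taken as completer means, they differ by 2.7.
- Loss in the active arm only: (40/45) × 3.6 − 0.9 = 2.30.
- Loss in both arms: (40/45) × (3.6 − 0.9) = 2.40.
- Loss in the placebo arm only: 3.6 − (40/45) × 0.9 = 2.80.

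If the lost active subjects are instead given the placebo mean: (40 × 3.6 + 5 × 0.9)/45 − 0.9 = 2.40. The largest shift, 0.40 days, is 0.40/0.751 = 0.53 SE.

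**4. Power.** 2.30 days at 45 per arm and SD 3.36 has about 89% power. If the completer effect were only 2.13 days, giving lost active subjects the placebo mean yields 2.13 × 40/45 = 1.89 days and about 75% power.

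**5. Outcome-dependent dropout (simulation).** Assumptions, not document figures: true difference 2.70; SD 3.36 each month; monthly mean reductions 1.2, 2.4, 3.6 (active) and 0.9 throughout (placebo); within-subject correlation 0.4 to 0.8; logistic dropout slope 0.2 to 0.4; dropout 11.1% or 12.5%. In the one-arm cases dropout is random in the other arm. The model column is a regression on months 1 and 2, standing in for a mixed model; for month-2 dropout it is one range over all three patterns.

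| Dropout depends on | Pattern | Available-case | Model |
|---|---|---|---|
| Month-2 reduction | Active arm only | 2.80 to 3.07 | 2.70 to 2.71 |
| Month-2 reduction | Placebo arm only | 2.33 to 2.60 | 2.70 to 2.71 |
| Month-2 reduction | Same rule, both arms | 2.56 to 2.68 | 2.70 to 2.71 |
| Month-3 reduction | Active arm only | 2.94 to 3.17 | 2.77 to 3.07 |
| Month-3 reduction | Placebo arm only | 2.23 to 2.46 | 2.33 to 2.63 |
| Month-3 reduction | Same rule, both arms | 2.38 to 2.60 | 2.44 to 2.67 |

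The largest available-case shift is 0.37/0.751 = 0.49 SE for month-2 dropout and 0.47/0.751 = 0.63 SE for month-3 dropout.

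**6. Unrecorded days, if counted as zero.**
- Three missing days under-count a month by 4 × 3/28 = 0.43 to 14 × 3/28 = 1.50 days over the entry range of 4 to 14.
- If everyone in both arms missed 3 days in month 3, 2.70 × 25/28 = 2.41.
- If one arm alone did, at an assumed baseline of 7.8 days: active only, 2.70 + 4.2 × 3/28 = 3.15; placebo only, 2.70 − 6.9 × 3/28 = 1.96.

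The one-arm cases are extremes. A systematic baseline difference between arms is not expected, because allocation follows the baseline diary.

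**The case against.** The best counter-reading is that the 25-entry rule was meant for the per-protocol set. It follows the per-protocol clause directly, and section 8 later says that treatment compliance alone decides per-protocol inclusion for outcomes that do not depend on the diary. Ambiguous drafting is possible. But the sentence as written covers analysis of the primary endpoint without qualification, and on either reading there is no rule for missing month-3 data. The generalized linear mixed model in section 7 relates daily headache probability to cumulative treatments and does not fill that gap.

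A second objection is that the shifts are small. That stands: one identical month-2 dropout rule moves 2.70 only to 2.56 to 2.68, and larger shifts need stronger assumptions.

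Some stronger readings are tempting but unsupported.

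- **Bias in favour of the device.** The direction depends on who leaves and from which arm.
- **An underpowered trial.** Nothing here shows that at the effect the sponsor expects. A 12.5% loss with 35 analysed per arm would conflict with a target counted in completers.
- **Unrecorded days count as headache-free.** The text is silent on scaling. The Definitions call a day headache-free only when the pain score is zero.
- **Subjects above 14 headache days leave the primary comparison.** Section 2 does not say so. It refers to grouping in the final study analysis, while sections 4 and 7 treat the first period as a complete trial analysed earlier.

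**Conclusion.** The concern holds. The primary analysis is a diary-completer analysis under an intent-to-treat label, the per-protocol comparison shares the same diary rule, and no planned analysis covers the subjects left out.

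On the stated assumptions (5 first-period losses per arm beyond 40 completers, and no reduction in those lost), about 11% of randomized subjects are missing and 2.7 days becomes 2.30 to 2.40, or 2.80 if losses occur in the placebo arm only. At first-trial effect sizes the issue is validity of the estimate rather than power. It should still be corrected before analysis, because it concerns the only primary comparison and the plan offers no way to judge the error.

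The missing scaling rule and the unclear status of subjects above 14 headache days are lesser points for clarification.

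**What to change.** Revise section 8 as follows.

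1. Define the primary set as all randomized subjects in their assigned arm.
2. Make the primary analysis a mixed model for repeated measures on the month 1 to 3 diary counts, with the month-3 contrast of BID active versus BID placebo as primary.
3. Express each month's count, including baseline, per 28 recorded days (count × 28 / entries). State the minimum number of entries for a usable month. A month below it is treated as missing, and the subject stays in the set.
4. Add one sensitivity analysis that assigns subjects without usable month-3 data no change or a placebo-like change. It is also needed for anyone who leaves before a usable month-1 diary and so has no post-baseline value.
5. Keep the 25-entry analysis as supportive and label it diary-completer.
6. As a secondary clarification, state that subjects above 14 headache days in a treatment month stay in the primary comparison and that their separate grouping is descriptive only.

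**Cost.** Daily diaries are already collected, so the work is a revision of section 8 and some programming. The primary method does change, from a t test or Mann-Whitney test to a model. The model relies on data being missing at random; when dropout depends on month 3 itself, the simulation shows that it removes only part of the shift. The estimate may move in either direction.
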